**I. Purpose, Background and Rationale**

**A. Aim and Hypotheses**

1. Use of electronic cigarette (e-cigarette) and heat-not-burn (HNB) products is continuing to proliferate in the US. In fact, e-cigarette use is expected to surpass combustible cigarette smoking rates in the next two years. The US FDA has regulatory authority to set appropriate product standards for e-cigarettes and heat-not-burn products with the goal of maximizing public health. Initial data suggest that these products present reduced harm compared to combustible cigarette smoking, but the comparative abuse liability and interest in use by smokers, particularly as a function of product flavor, remains largely unknown. These questions are critical in helping the FDA impose meaningful and effective regulations on these products. African American (AA) smokers are showing increased interest in these new and emerging products. Research suggests AA smokers take larger puffs and inhale more deeply than whites. Therefore, data are needed to understand if AA smokers will also use e-cigarettes and HNB devices in such a way that could inadvertently increase harm in the long run. Additionally, research is urgently needed to understand whether these products (if shown to be less harmful than cigarettes), would be an acceptable alternative to traditional smoking and how product flavor (tobacco vs. menthol) impacts use patterns and preference. The current study is not a cessation study and does not aim to induce long-term uptake of the study products. The objective of the study is to test the acute pharmacokinetic profile of these products during a 65-minute use period with each product across three to four study visits.

2. Aim 1: Understand the abuse liability of heat-not-burn devices, e-cigarettes, and combustible cigarettes in terms of nicotine delivery, puff patterns (topography), and reductions in nicotine withdrawal/craving. H1: Combustible cigarettes will show the fastest and greatest nicotine delivery, followed by e-cigarettes, and heat-not-burn devices. H2: Topography measures will be greatest for cigarettes, followed by e-cigarettes, and heat-not-burn devices. H3: Use of cigarettes will be associated with the greatest reduction in symptoms of nicotine withdrawal and craving.

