Aim 2: Examine resultant toxicant exposure of heat-not-burn devices, e-cigarettes, and combustible cigarettes. H1: Exhaled carbon monoxide will be greatest for cigarettes, followed, by heat-not-burn devices and e-cigarettes (no exposure).

**Aim 3:** Understand the comparative acceptability of tobacco and menthol flavored e-cigarettes among menthol cigarette smokers. H1: Menthol cigarette smokers will show increased topography measures when using the menthol (vs. tobacco) flavored e-cigarette. H2: Menthol cigarette smokers will show increased acceptability and more positive subjective effects when using the menthol (vs. tobacco) flavored e-cigarette.

**Exploratory Aim:** Understand differences in abuse liability of e-cigarettes, HNB products, and cigarettes as measured behaviorally in a concurrent choice task.

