**C. Sample size, statistical methods, and power calculation**

1. 20 eligible AA and white smokers will be randomized. We will use a 1:1 fashion randomization to product order (combustible cigarette, e-cigarette, heat-not-burn device vs. combustible cigarette, heat-not-burn device, e-cigarette). Randomization will be determined by computer-generated random numbers. Randomization assignments will be placed in sealed envelopes with sequential study ID numbers. After baseline data collection has been completed, the research assistant will select the sequential study ID number to determine the randomization assignment
2. No blinding is involved in the first three study visits. For participants who complete the fourth visit (flavor assessment), participants and research assistants that interact with participants will be blind to flavor (double blind design).
3. Due to the pilot nature of the current study, a primary aim of the study is to collect data for power calculations for a fully powered trial. Therefore, formal power calculations were not conducted. ANOVAs will be conducted to detect within-subject differences between products for all outcomes. A Bonferroni correction will be applied to adjust for multiple comparisons. A paired samples t-test will be conducted to detect differences in outcomes in the e-cigarette flavor assessment.

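### Bonferroni in II.C.3 has no stated alpha or family; Holm gives the same error control, is never less powerful, and helps materially if effects are moderate

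*Combined protocol and SAP*

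**What the plan says.** Section II.C, item 1, fixes the sample: "20 eligible AA and white smokers will be randomized". Each participant uses all three products. Item 3 sets the analysis: "ANOVAs will be conducted to detect within-subject differences between products for all outcomes", followed by "A Bonferroni correction will be applied to adjust for multiple comparisons". The same item says "formal power calculations were not conducted", because the study is a pilot and "a primary aim of the study is to collect data for power calculations for a fully powered trial".

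Alpha, sidedness and the family of comparisons are not given. Section V.A adds that nicotine delivery is compared across products at each timepoint, and the laboratory tests item lists five blood draws per visit. Section V.B names nicotine delivery as the primary endpoint.

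The hypotheses in section I.A are of two kinds:

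- **Full rankings.** Aim 1 H1: "Combustible cigarettes will show the fastest and greatest nicotine delivery, followed by e-cigarettes, and heat-not-burn devices". Aim 1 H2 gives the same order for topography. Aim 2 H1 gives a different order: "Exhaled carbon monoxide will be greatest for cigarettes, followed, by heat-not-burn devices and e-cigarettes (no exposure".
- **A top rank only.** Aim 1 H3 predicts that cigarettes produce the greatest relief of withdrawal and craving, and does not rank the other two products.

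**The concern.** A ranking of three products is supported only if both adjacent contrasts hold: first over second, and second over third. The relevant power is the joint power of two tests, which falls faster than the power of either test as the per-test threshold tightens. Bonferroni holds every pair to the strictest threshold, even after other pairs have been rejected. Holm relaxes the threshold after each rejection and still controls the familywise error under the same conditions. With 20 participants and no power calculation, the plan may give up power for its ranking hypotheses without gaining any error control.

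The undefined family adds to this. A reader cannot tell whether the correction covers three product pairs, three pairs at each of five draws, or every outcome. For the primary endpoint these choices give very different thresholds.

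**Working it through.** The plan states no power, alpha or effect size, so it has no figure to reproduce.

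**Inputs from the documents.** n = 20, within-subject, three products, so three product pairs; five blood draws per visit.

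**Assumptions.** Two-sided familywise alpha 0.05; a family of three pairs unless stated otherwise; no dropout; paired t-tests with 19 degrees of freedom; equal variances and correlations across the three sessions. The effect dz is the mean paired difference divided by the SD of the paired differences, and it is varied because the documents do not give it.

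**Thresholds.**
- Bonferroni: 0.05/3 = 0.0167 for each pair.
- Holm: smallest p-value against 0.05/3 = 0.0167, the next against 0.05/2 = 0.025, the largest against 0.05, stopping at the first failure.

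Both start at 0.0167, so the chance of at least one rejection is identical. After that, Holm's thresholds are never stricter.

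**Power of one pair.** Power = P(T > t_crit), where T is noncentral t with 19 df and noncentrality dz × √20 (the opposite tail is negligible). For dz 0.8 the noncentrality is 0.8 × 4.472 = 3.58. The critical values are 2.093 at 0.05 and 2.625 at 0.0167.

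| dz | at 0.05 | at 0.0167 |
|---|---|---|
| 0.5 | 56.4% | 37.3% |
| 0.8 | 92.4% | 81.8% |
| 1.0 | 98.9% | 95.8% |

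**Chance of confirming the full order.** Both adjacent contrasts must be significant in the stated direction. This was simulated with 40,000 data sets per row.

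| Adjacent dz (upper step, lower step) | Bonferroni | Holm | Gain (points) |
|---|---|---|---|
| 0.3, 0.3 | 0.3% | 1.8% | 1.5 |
| 0.4, 0.4 | 2.1% | 8.2% | 6.1 |
| 0.5, 0.5 | 8.2% | 23.3% | 15.1 |
| 0.6, 0.6 | 22.3% | 46.2% | 23.9 |
| 0.7, 0.7 | 43.5% | 68.7% | 25.2 |
| 0.8, 0.8 | 64.6% | 84.5% | 19.9 |
| 1.0, 1.0 | 91.6% | 97.6% | 6.0 |
| 1.2, 1.2 | 99.0% | 99.8% | 0.8 |
| 1.5, 0.5 | 37.1% | 55.9% | 18.8 |
| 1.5, 0.8 | 81.7% | 92.5% | 10.8 |
| 0.8, 0.3 | 7.5% | 19.7% | 12.2 |

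Every Bonferroni rejection was also a Holm rejection in all simulated data sets, as theory requires. The unequal rows show that one large step does not remove the gain, because the smaller step decides whether the order is confirmed. The same figures apply to any three-product order, including the different one for exhaled carbon monoxide.

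**Benchmark.** If the joint claim that both adjacent differences hold were the only claim made, each could be tested at 0.05 without correction (an intersection-union test). At dz 0.8 that gives 84.6%, almost the same as Holm.

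**Effect of the family.** If the correction covered three pairs at five draws, the threshold would be 0.05/15 = 0.0033. At dz 0.8, the power of one pair would fall from 81.8% to 59.4%.

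**The case against.** Bonferroni is valid and conservative, and nothing in the plan inflates an error rate. The study is a declared pilot that makes no power claim. For a pilot, estimates and intervals matter more than confirming an order, and Bonferroni has simple matching simultaneous intervals, which Holm lacks. All of this stands and is why the point is minor. It does not make Bonferroni preferable for the tests: the plan still states directional rankings and commits to adjusted testing.

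A second objection is that the size depends on an effect the documents do not give. This also stands. The gain peaks near equal steps of 0.6 to 0.8 and is small at 0.3, where both methods almost always fail, and at 1.0 or above, where both usually succeed. Equal steps also make the third contrast twice as large as each adjacent one, which helps Holm to relax its threshold early.

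A third is that the three-pair family is an inference. That is correct, and defining the family may matter as much as the choice of method.

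A reader might also infer that e-cigarette versus heat-not-burn is the closest contrast and so the most likely to be lost. The documents do not support this. The literature review in I.B cites one study in which the e-cigarette's nicotine delivery was comparable to a cigarette's and another in which it came near without reaching it. Cigarette versus e-cigarette could equally be the closest pair.

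**Conclusion.** The point holds as a minor, inexpensive improvement. Bonferroni is never more powerful than Holm at the same familywise error, and II.C.3 leaves alpha and the family open. With 20 complete participants, three pairs and two-sided 0.05, Holm adds about 15 to 25 points to the chance of confirming a full order for equal adjacent dz of 0.5 to 0.8, 6 points at 1.0, and under 2 points at 0.3 or 1.2. All of these rest on assumed effect sizes.

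Two stronger readings are tempting. One is that the correction sharply cuts the study's power in general. The documents give no effect size from which to conclude that, and the chance of at least one rejection is the same under both methods. The other is that the plan contains a statistical error. It does not: the stated correction protects the familywise error once its family is defined.

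**What to change.** In II.C.3, replace the Bonferroni sentence with one that specifies Holm step-down at two-sided familywise 0.05 over the three product pairs within each endpoint. For nicotine, state whether the family is the three pairs within each timepoint or within one named primary timepoint. Separate families per timepoint do not control error across the draws; a single named timepoint avoids that for the primary claim.

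Add that an order hypothesis is claimed only if both adjacent contrasts are significant in the stated direction, using the order given for that endpoint.

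The cost is one or two sentences, with no change to design, sample or data collection. The downside is that Holm has no simple matching simultaneous intervals, so report ordinary 95% intervals beside the Holm-adjusted p-values and label them as unadjusted.

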Participants who report typically smoking menthol cigarettes will be invited to complete a fourth session. Participants will undergo overnight tobacco/nicotine abstinence before the visit (eCO2≤12ppm). Participants will then be randomized 1:1 to e-cigarette flavor order (tobacco e-cigarette, menthol e-cigarette) and will complete sessions in a counterbalanced fashion to control for order effects. They will complete a 30-minute ad libitum session with the first product, based on randomization, followed by a 1.5-hour standard washout period, followed by a 30-minute ad libitum vaping session with the second product (menthol or tobacco flavor). Throughout each session, puff topography will be measured via a pressure sensor attached to the e-cigarette device. Participants will complete self-report measures of smoking urges and withdrawal symptoms pre- and post-

vaping session. In addition, they will complete measures of subjective vaping experience, perceptions of flavor, product demand, and intentions for future use.

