- f. **Visit three:** Aside from the product being used, the first portion of visit three will closely mirror visits one and two. Participants will complete baseline self-report measures regarding their practice period (product liking/evaluation and preferences). Participants will again complete CO measurement to confirm tobacco/nicotine abstinence. They will complete a PK and ad-lib session identical to visits one and two. Following the PK and ad-lib sessions, participants will have a 1.5-hour washout/rest period in order to bring them to a state of nicotine deprivation. During the washout period, participants will be allowed to watch a movie or listen to music. Participants will then complete a concurrent choice task with their usual brand cigarette, e-cigarette, and HNB device. In the task, participants will earn puffs of the various products by clicking a mouse/keyboard a set number of times. The participants will be free to choose how they allocate the puffs between the available products. For each task, participants can earn up to 20 puffs and the task will last up to 1.5 hours. Puff topography will be measured throughout the task. The objective of the task is to behaviorally measure whether or not participants see the e-cigarette and/or HNB device as an acceptable or preferable substitute for their usual brand cigarette. Participants will be compensated \$100 for visit

three. In addition, participants will earn up to \$50 for completing all study visits (see section III.G.). We anticipate that visit three will last no more than 4.5 hours.

i. **Computer task:** The usual brand cigarette, e-cigarette, and HNB product are all available. Participants will earn puffs of the products by clicking boxes on a computer screen that represent the products. To earn 1 puff of a product, the participant will be instructed that they must click the corresponding box. In order to earn puffs of the e-cigarette or HNB product, they will click the corresponding box 10 times. To test relative demand for their usual brand cigarette, it will be placed on a variable ratio, meaning the number of clicks necessary to earn puffs of the usual brand cigarette will increase with each trial of the task. Once participants earn a puff, they will be given two minutes to have the puff before the next trial begins.

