**Computer screen simulation for task:**

[figure not shown]
g. Visit four (menthol smokers only): Participants who report typically smoking menthol cigarettes will be invited to complete a fourth session. Participants will undergo overnight tobacco/nicotine abstinence before the visit ( $eCO \leq 12 \text{ ppm}$ ). Participants will then be randomized 1:1 to e-cigarette flavor order (tobacco e-cigarette, menthol e-cigarette). They will complete a 30-minute ad libitum session with the first product, based on randomization, followed by a 1.5 hour standard washout period, followed by a 30-minute ad libitum vaping session with the second product. Throughout each session, puff topography will be measured via a pressure sensor attached to the e-cigarette device. Participants will complete self-report measures of smoking urges and withdrawal symptoms pre- and post-vaping session. In addition, they will complete measures of subjective vaping experience, perceptions of flavor, product demand, and intentions for

future use. We anticipate that the session will last ~3 hours.

Participants will earn \$50 for attending the study visit.

h. **Six-month follow-up:** Six months after completion of visit 3 (or study discontinuation), participants will be contacted by phone to assess ongoing use of study products. Three attempts will be made to contact the participant for this follow-up. If they endorse ongoing use, they will be advised to quit all tobacco use and offered a referral to the Quitline. We anticipate this phone follow-up to last no more than 10 minutes. This follow-up assessment is for safety monitoring only.

3. Due to COVID-19 and the need to keep patients and researchers safe, we will use Zoom, a HIPAA compliant, university approved video conferencing software, during the visit. This will allow the participant to smoke freely (unmasked) while the researcher can watch and communicate with the participant via video conferencing from outside the clinic room. We will utilize Zoom as much as possible and only enter the room when absolutely necessary.
4. All tests, procedures, and visits are being performed solely for research purposes and are not billable to insurance companies.

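### Visit 4 randomises flavour order to control for order effects, but the planned paired t-test does not use order and no way of securing near-equal orders is stated; a blocked list and, from about 10 completers, a period term would be a cheap improvement

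*Combined protocol and SAP*

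**What the plan says.** All places are in the Combined protocol and SAP.

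- **Who.** Section II.C, item 1: "20 eligible AA and white smokers will be randomized". Section II.B: "Participants who report typically smoking menthol cigarettes will be invited to complete a fourth session". The number of menthol smokers is not given, so visit 4 has at most 20 participants and may have far fewer.
- **Design.** Sections II.B and II.E.2.g randomise participants 1:1 to flavour order. Each has a 30-minute session with one flavour, "followed by a 1.5 hour standard washout period, followed by a 30-minute ad libitum vaping session with the second product". Section II.B adds that participants "will complete sessions in a counterbalanced fashion to control for order effects".
- **Analysis.** Section II.C, item 3: "A paired samples t-test will be conducted to detect differences in outcomes in the e-cigarette flavor assessment". Section V.A adds no visit 4 analysis. No section names a period, order or sequence term.
- **Allocation.** The computer-generated numbers and sealed envelopes in section II.C, item 1 are described for product order in visits 1 to 3, where "the research assistant will select the sequential study ID number to determine the randomization assignment". No block size or other restriction is given there, and no list is described for flavour order. Item 2 makes visit 4 double blind: participants, and the research assistants who deal with them, do not know the flavour.
- **Washout.** Section II.E.2.f gives the same interval at visit 3 a purpose: a "1.5-hour washout/rest period in order to bring them to a state of nicotine deprivation".

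**The concern.** In a two-period crossover, outcomes may differ between the first and second session whatever the flavour, for example through fatigue, practice or residual nicotine. Randomising the order guards against this, but an analysis that ignores order pays for it in one of two ways.

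- If the orders are equal, the period difference cancels from the mean flavour difference. It stays in the SD of the differences, so the confidence interval is too wide and power falls.
- If the orders are unequal, part of the period difference also remains in the flavour estimate.

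At stake are the precision of the flavour comparison and the SD carried forward. Section II.C, item 3 says that a primary aim of this pilot is to supply data for powering a later trial, and an SD from raw paired differences includes any period effect.

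**Working it through.** The plan states no power, SD or effect for visit 4, so there is no figure to reproduce.

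**Assumed inputs.** Two-sided 0.05 and one outcome. The unit is the SD of the within-person flavour difference within one order. The flavour effect δ is 1 (0.5 as a check). The period effect π is 0, 0.25, 0.5 or 1. Visit 4 n runs from 4 to 20, where 20 is the documents' ceiling.

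**Model.** The flavour difference for one person is d = δ + π in one order and δ − π in the other, plus N(0,1) error. The orders contain n1 and n2 people, with n = n1 + n2.

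**Paired t-test** (n − 1 df).
- Expected estimate: δ + π(n1 − n2)/n.
- With equal orders the expected variance of d is 1 + π²n/(n − 1). At n=10 this is 1 + 0.25 × 10/9 = 1.28 for π = 0.5 (SD 1.13), and 1 + 10/9 = 2.11 for π = 1 (SD 1.45).

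**Period-adjusted analysis** (n − 2 df).
- Estimate: the average of the two orders' mean differences. It is free of π, with SE = ½√(1/n1 + 1/n2).
- At 5:5 the SE is ½√0.4 = 0.316, the same as the paired test with no period effect. The cost is only the critical value, 2.306 instead of 2.262.

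**Power with equal orders, δ = 1** (noncentral t for the adjusted analysis; numerical integration over a noncentral chi-square for the paired test):

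| n | Adjusted | Paired, π=0 | π=0.25 | π=0.5 | π=1 |
|---|---|---|---|---|---|
| 4 | 22% | 29% | 27% | 21% | 9% |
| 6 | 46% | 51% | 48% | 40% | 19% |
| 10 | 79% | 80% | 78% | 72% | 48% |
| 14 | 93% | 93% | 92% | 89% | 72% |
| 20 | 99% | 99% | 99% | 98% | 92% |

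With δ = 0.5 the pattern is the same: 29% against 29 / 27 / 22 / 9% at n=10, and 56% against 56 / 54 / 47 / 25% at n=20.

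**Interval width.** The mean 95% half-width at n=10 is 0.71 adjusted, against 0.70 / 0.72 / 0.79 / 1.02 paired.

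**Break-even.** The period effect above which adjusting gains power (δ = 1) is 0.32 SD at n=6, 0.24 at n=8, 0.20 at n=10, 0.15 at n=14 and 0.11 at n=20.

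**Unequal orders, relevant only if the list is unrestricted.**
- At n=10 an exact 5:5 split has probability 25%, and 7:3 or worse 34%.
- At 7:3 the paired estimate shifts by π × (7 − 3)/10 = 0.4π, that is 0 / 0.10 / 0.20 / 0.40 SD.
- With π = 0.5 the paired test's type I error is 3.0% at 5:5, 6.1% at 7:3 and 10.6% at 8:2. Averaged over all splits it is 5.0%.
- Adjusting at 7:3 has a cost too: SE = ½√(1/7 + 1/3) = 0.345, and power is 72% against 80% for the paired test if π = 0. This is why the list and the model belong together.

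**The case against.** The strongest reply is that nothing is broken. Counterbalancing is control by design. With equal orders a period effect cancels from the mean, so the purpose stated in section II.B is met without any model term, and that section promises no model adjustment. This stands: the loss is of efficiency, not validity.

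A reader might infer that the paired test is biased or produces excess false positives. The documents do not support that. With equal orders the test is conservative, and averaged over simple 1:1 randomisation its size is near 5%. Nor do they show that orders will be unequal: the list is nowhere called unrestricted, and the counterbalancing wording suggests that balance is intended. What is missing is the method.

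A reader might also see a conflict between the envelope procedure and the visit 4 blind. There is none. The envelopes are described for product order, and the blind covers only research assistants who interact with participants, so other staff could hold the flavour list. The procedure simply needs its own wording for visit 4.

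The benefit also depends on a period effect that the documents do not give. If the 1.5-hour interval restores deprivation, as intended at visit 3, the effect may be small and little would change. That is fair. It is equally fair that visit 4 may have fewer than 10 participants, where a period term can cost more than it returns. An unconditional switch of analysis is therefore not justified.

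Finally, the stakes are low. This is a pilot without a power calculation, the primary endpoint in section V.B is nicotine delivery, and a period-adjusted SD can be computed later if order is recorded. Blocking, however, cannot be added after randomisation.

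**Conclusion.** The point holds as a cheap improvement, to be considered. The plan randomises flavour order for a stated reason, does not use order in the analysis, and does not say how near-equal orders are secured. The planned test remains valid.

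The trade-off is asymmetric from about n=10. At n=10 with δ = 1, adjusting costs about 1 power point if there is no period effect and gains about 7 points at 0.5 SD and 31 at 1 SD. Below about 0.2 SD there is little or no gain. In smaller samples the cost with no period effect rises to about 4 points at n=6 and 7 at n=4, so the change should depend on n. The threshold is gradual: at n=8 the cost is about 2 points.

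These sizes rest on assumed effects, SD and n. They also assume an additive period effect and equal carryover.

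**What to change.** 1. **Sections II.B and II.E.2.g.** Draw flavour order from a computer-generated list in small, randomly varied blocks, for example of 2 and 4. Conceal the list and block sizes from participants and from the staff who interact with them. With the two sizes equally likely, such a list gives 5:5 in 89% of cases at n=10 and 6:4 otherwise.
2. **Section II.C, item 3.** Pre-specify that if at least about 10 participants complete visit 4 (the number to be fixed without looking at outcomes), flavours are compared in a model with flavour and period as fixed effects and participant as block. Report the flavour difference, its 95% CI and the period-adjusted within-person SD. With fewer completers, keep the paired t-test as the main analysis and report the period-adjusted estimate as a sensitivity analysis.
3. **Same item.** State that carryover after the washout is assumed equal for the two flavours, because a period term does not remove unequal carryover.

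**Cost.** A few sentences, a concealed list and one degree of freedom. At n=10 and δ = 1, both changes together, against the paired test under simple randomisation, change power by −1 / +1 / +8 / +29 points at period effects of 0 / 0.25 / 0.5 / 1 SD.
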